5.3.2 Causality collection

The Investigator will assess causal relationship between the IPs and each AE and answer “yes” or “no” to the question “Do you consider that there is a reasonable possibility that the event may have been caused by the investigational product?”

For SAEs causal relationship will also be assessed for other medications and study procedures. For SAEs that could be associated with any study procedure, the causal relationship is implied as “yes.”

5.3.3 Relationship to protocol procedures

The Investigator is also required to provide an assessment of the relationship of SAEs to protocol procedures on the SAE report form. This includes both non-treatment–emergent (i.e., SAEs that occur prior to the administration of IP) and treatment-emergent SAEs. A protocol-related SAE will be used as a result of a procedure or intervention required during the study (e.g., blood collection). The following guidelines will be used by the investigators to assess the relationship of SAEs to the protocol:

- Protocol related: The event occurred due to a procedure or intervention that has been described in the protocol for which there is no alternative etiology present in the patient’s medical record.

- Not protocol related: The event is related to an etiology other than the procedure or intervention that is described in the protocol. The alternative etiology must be documented in the study patient's medical record.

5.3.4 Adverse events based on signs and symptoms

All AEs spontaneously reported by the patient or reported in response to the open question from the study personnel: "Have you had any health problems since the previous visit/you were last asked?" or revealed by observation will be collected and recorded in the eCRF. When collecting AEs, the recording of diagnoses will be preferred, when possible, to recording a list of signs and symptoms. However, if a diagnosis is known and there are other signs or symptoms that are not generally part of the diagnosis, the diagnosis and each sign or symptom will be recorded separately.

5.3.5 Adverse events based on examinations and tests

The results from protocol-mandated laboratory tests and vital signs measurements will be summarized in the Clinical Study Report (CSR). Deterioration as compared to baseline in protocol-mandated laboratory values and vital signs will be reported as AEs if they fulfill any of the SAE criteria or are the reason for discontinuation of treatment with the IPs.

If deterioration in a laboratory value or vital sign will be associated with clinical signs and symptoms, the sign or symptom will be reported as an AE and the associated laboratory result or vital sign will be considered as additional information. Whenever possible, the reporting Investigator will use the clinical rather than the laboratory term (e.g., anemia versus low hemoglobin value). In the absence of clinical signs or symptoms, clinically relevant deteriorations in non-mandated parameters will be reported as AEs.

Any new or aggravated clinically relevant abnormal medical finding at a physical examination as compared with the baseline assessment will be reported as an AE.

5.3.6 Deaths

All deaths that will occur during the study treatment period, or within the protocol-defined follow-up period after the administration of the last dose of study drug, will be reported to the Study Monitor/Physician as a SAE within 24 hours. It will be also documented in the eCRF.

Sponsor has the right to request additional information for any patient with ongoing AE(s)/SAE(s) at the end of the study, if judged necessary.

5.3.7 Follow-up of unresolved adverse events

Any AEs that are unresolved at the patient's last visit in the study will be followed up by the investigator for as long as medically indicated, but without further recording in the eCRF. After 30 days from last treatment, only patients with ongoing investigational product-related SAEs will continue to be followed for safety.

Sponsor has the right to request additional information for any patient with ongoing AE(s)/SAE(s) at the end of the study, if judged necessary.

5.3.8 Reporting of serious adverse events

All SAEs will be reported, whether or not considered causally related to the investigational product, or to the study procedure(s). The reporting period for SAEs will be the period immediately following the time that written informed consent will be obtained through 30 days after last treatment or until the initiation of alternative therapy. The investigator and/or Sponsor will be responsible for informing the Ethics Committee and/or the Regulatory Authority of the SAE as per local requirements.

The sponsor will also indicate the causality of events in relation to all study medications, as determined by the principal investigator. A SAE report will be sent via email to the safety desk within 24 hours.

5.3.9 Reporting of Suspected Unexpected Serious Adverse Reactions

Fatal or life-threatening suspected unexpected serious adverse reactions (SUSARs) will be reported by the Sponsor to the concerned regulatory Authority(ies) and to the Ethics Committee, within 7 calendar days after knowledge according to applicable regulations. The relevant follow-up information will be subsequently communicated within an additional 8 days.

All other SUSARs will be reported by the Sponsor to the concerned regulatory Authority(ies) and to the Ethics Committee with expedited reporting, within a maximum of 15 calendar days of first knowledge. The relevant follow-up information will be subsequently communicated as soon as possible.

The Sponsor will also inform all Investigators.

5.4 Pregnancy

Pregnancies and suspected pregnancies (including a positive pregnancy test regardless of age or disease state) of a female subject occurring while the subject is on investigational products, or within one month of the subject's last study treatment, will be considered immediately reportable events. Treatment will be discontinued immediately. The pregnancy, suspected pregnancy, or positive pregnancy test will be reported to the sponsor immediately using pregnancy the Reporting Form. The Investigator will follow the female subject until completion of the pregnancy, and will notify to the StudySponsor immediately about the outcome of the pregnancy (either normal or abnormal outcome). If the outcome of the pregnancy will be abnormal (e.g., spontaneous or therapeutic abortion), the Investigator will report the abnormal outcome as an AE. If the abnormal outcome meets any of the serious criteria, it will be reported as an SAE within 24 hours of the Investigator's knowledge of the event using the SAE Report Form, or approved equivalent form.

6. SAMPLE SIZE AND STATISTICAL METHODS

ACIGAN. Data from the literature (22,23) have shown a difference in renal survival between corticosteroids and controls when the researchers assumed a difference of 50% in the primary end point (i.e. in the between-arms difference of delta 24 hour proteinuria from baseline to 6 months) as clinically relevant. Therefore, we assume that a mean delta proteinuria from baseline to 6 months in patients treated with RASBs alone (control arm) is 0.6 ± 1.0 g/24 hours (\pm SD) versus a mean delta proteinuria that is 1.2 ± 1.0 g/24 hours (\pm SD) from baseline to 6 months in patients treated with RASBs and corticosteroids (experimental arm). Based on these assumptions, we calculated a sample size of

132 patients (66 patients per group including a 10% dropout rate) for a power of 90%, a two-sided significance level of 0.05 and 3 years of recruitment. If the number of the enrolled patients will be insufficient, the recruitment period will be extended for two years.

CHRONiGaN. Data from the literature (29-31) have shown a difference of renal survival between SGLT2is and controls. There are no data in the literature exploring the difference of renal survival or proteinuria between SGLT2is and steroids. Here, the researchers assumed an opportunistic sample of 300 patients for this first comparative study (150 patients per group, including a 10% dropout rate).

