3. TRIAL DESIGN

This project encompasses two prospective, multicentre, open-label randomized controlled clinical trials (RCTs) of IgAN patients (CLlGaN) based on the kidney biopsy report (*Figure 1*).

Stratified randomization will be done by age and sex in renal centers.

[figure not shown]

Figure 1

ACiGaN TRIAL

Patients with active renal lesions (E1 and/or C1) in the presence of $GFR \geq 30$ ml/min/1.73 m² and proteinuria ≥ 0.5 g/24 hours will be randomized into two arms:

- 1) corticosteroids combined with RASBs for 4 months followed by RASBs alone (experimental arm);
- 2) RASBs alone for 4 months followed by the combination corticosteroids and RASBs for 4 additional months and then only RASBs (standard care) as suggested by KDIGO guidelines (5).

Participants assigned to the experimental arm will receive by 2 weeks from the kidney biopsy (pulse) methylprednisolone (SOLU-Medrol) 500-1000 mg in the first day and then 50% of dose in the next two days followed by oral prednisone (0.5 mg/kg/bw) on alternate days until the end of the month. This treatment will be repeated for three consecutive months. After three months, participants will gradually reduce oral prednisone, in the course of four weeks. Next, they will receive RASBs alone.

The daily dose of methylprednisolone will be individualized (15 mg/kg), based on the ideal body weight. The drug will be administered in a single dose intravenously for 30-60 min. To avoid obesity and diabetes corticosteroids will be administered only in the morning.

This is a parallel group, two arm, superiority trial with 1:1 allocation ratio.

As per standard care RASB therapy will be titrated to its maximum labelled or tolerated dose as anti-proteinuric effect in every patient.

Rationale of the study design

Corticosteroids at high dosage have been administered in RCTs of IgAN (18,41) independent of the type of renal lesions despite empiric evidence from clinical practice and strong and consistent evidence from observational studies that the lesions identified at kidney biopsy may play a role in the response to treatment. Our aim is to evaluate the benefit of early pulse therapy combined with oral prednisone only in IgAN patients with active renal lesions. In our protocol, we have excluded intensive immunosuppressive therapy (CS+CYP/AZA/MMF) because RCTs have demonstrated that the potential benefits-harms trade off is in favour of the harms (42).

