4.4 Outcome measures

The primary endpoint is the 24 h-proteinuria reduction between arms as suggested by Inker LA et al (44). It will be assessed after 4 and 8 months in the ACiGaN study and after 10 months in the CHRONiGaN trial.

The secondary end point is the GFR slope calculated as the mean of individual slope obtained from individual linear regression of eGFR overtime (3 years). Based on the International Consensus definition of clinical trial outcomes for kidney failure (23) we have also considered other secondary end points listed below.

Primary and secondary end points that will be evaluated in the two RCTs are listed below:

Primary endpoint:

- Between-arms difference in proteinuria reduction within 4 and 8 months in ACiGaN and within 10 months in CHRONiGaN study.

Secondary endpoints:

- eGFR slope calculated as mean of individual slope obtained from individual linear regression of eGFR overtime (3 years);
- eGFR decline > 40 % from the baseline value;
- composite end point: GFR decline > 40%, ESKD (defined as long-term GFR \leq 15 ml/min/1.73m² for more than three months or need for maintenance dialysis or kidney transplantation) or death due to kidney disease;
- absolute difference between last GFR value and baseline GFR;
- stable renal function defined as a decline in GFR \leq 5 ml/min/1.73m² at the end of three years follow-up;
- mean annual change in the slope of the reciprocal of serum creatinine concentration;
- time-averaged proteinuria (TA-P) calculated as the weighted mean of all post-randomization measurement, with weights representing the time elapsed since the previous measurement;
- proteinuria slope, calculated as a mean of individual slope, obtained from individual linear regression of daily proteinuria overtime (3 years);
- complete remission of proteinuria defined as achievement of urinary protein level \leq 0.2 g/day or a urinary protein-to-creatinine ratio \leq 0.2 g/g;
- partial remission of proteinuria defined as achievement of a urinary protein reduction \geq 50% or greater compared with baseline value.

The end points will be evaluated monthly in IgAN patients with active renal lesions in the first eight months after kidney biopsy and then every three months. In IgAN patients with chronic or moderate renal lesions the end points will be evaluated every three months in the first two years after the enrollment and then every six months.

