6.4 Statistical Methods

Quantitative variables will be summarized in the presence of normal distribution values as mean \pm SD or median, and interquartile ranges in the presence of non-normally distributed variables. The between-arms comparisons of continuous variables will be performed by independent t-test or Mann-Whitney U test, as appropriate. The between-arms difference of the primary end point (i.e. in the between-arms difference of delta 24h proteinuria from baseline to 6 months in the ACiGAN trial and the between-arms difference of delta 24h proteinuria from baseline to 12 months in the CHRONiGAN trial will be expressed as mean difference and 95% CI. Categorical variables will be presented as absolute and percentage frequency. Proportions will be compared using the Pearson's X^2 test or Fisher's test, as appropriate. The time to event analysis will be performed by the Kaplan-Meier curves by comparing the experimental and control group by the log rank test. Multivariate analysis will be based on Cox's regression proportional hazard method and used to assess the relative risk associated with possible baseline prognostic factors such as sex, age, serum creatinine, eGFR, hypertension, histological lesions and therapy.

The primary analysis will be conducted according to the intention-to-treat approach in all randomized patients, irrespective of adherence to the assigned treatment. A per protocol analysis will be also performed. A secondary analysis by linear mixed models (LMM) or generalized estimating equations (GEE) of repeated measurements of eGFR and proteinuria will be also performed. The choice between the two analyses will closely depend on the distribution type of the outcome variables in our study cohorts.

In these models, data will be expressed as regression coefficients, 95% CIs and P value. All analyses will be performed using SPSS for Windows, 17.0 (SPSS Inc., North Sydney, Australia) and STATA/IC 13.1 for Windows (College Station, Texas, US). A *P* value less than 0.05 will be considered statistically significant.

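### ACiGaN's primary endpoint is set at 4 and 8 months but powered and analysed at 6 months against RASBs alone, a comparator the schedule need not maintain after month 4, so the 90% power is unsupported at the analysed time

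*Protocol*

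**What the plan says.** All references are to the protocol.

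**Endpoint.** Section 4.4 says of the primary endpoint, the reduction in 24-hour proteinuria: "It will be assessed after 4 and 8 months in the ACiGaN study and after 10 months in the CHRONiGaN trial". The synopsis gives 4 months, and 8 months in non-responders. Section 6.5 also uses 4 and 8 months to define the persistent population.

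**Sample size.** Section 6 assumes "a mean delta proteinuria from baseline to 6 months in patients treated with RASBs alone (control arm) is 0.6" g/24 h (SD 1.0) against "a mean delta proteinuria that is 1.2 ± 1.0 g/24 hours" "from baseline to 6 months in patients treated with RASBs and corticosteroids (experimental arm"). With 90% power, "a two-sided significance level of 0.05" and 10% dropout it arrives at 132 patients, 66 per arm. The synopsis repeats this.

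**Analysis.** Section 6.4 describes the primary comparison as lying "in the between-arms difference of delta 24h proteinuria from baseline to 6 months in the ACiGAN trial". Section 7.3 sets an interim analysis of the primary endpoint once half the patients have been randomised and have completed 6 months of follow-up; it does not say which trial this refers to.

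**Treatment schedule.** In Section 3 the ACiGaN control arm receives "RASBs alone for 4 months followed by the combination corticosteroids and RASBs for 4 additional months and then only RASBs". The experimental arm has corticosteroids with RASBs for the first 4 months and RASBs alone afterwards. The synopsis shows the same sequence. Section 1.2 differs: there, control patients receive corticosteroids after month 4 only if proteinuria is still at least 0.5 g/24 hours and eGFR at least 30 ml/min/1.73 m².

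**The concern.** There are two linked faults. First, the protocol carries two definitions of one primary endpoint: months 4 and 8 where endpoints are defined, month 6 where the trial is sized and analysed. Month 6 is not an endpoint time in Section 4.4 or the synopsis, and neither 4 nor 8 is the time analysed in Section 6.4.

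Second, the planning assumption describes the control arm at month 6 as on RASBs alone, while the schedule lets that arm start corticosteroids at month 4. At month 6, control patients who started are two months into their course and experimental patients have been off corticosteroids for two months.

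At stake are the confirmatory analysis of ACiGaN and its only power justification. With 4, 6 and 8 months all in the text of an open-label trial, the primary time could be settled after data have been seen. The interim look for benefit or futility takes over the same ambiguity.

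**Working it through.** **1. Reproduce the stated sample size.** Inputs from Section 6: difference δ = 1.2 − 0.6 = 0.6 g/24 h; σ = 1.0; two-sided α = 0.05; power 90%; dropout 10%. Allocation is 1:1 (Section 3).

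n per arm = 2(1.96 + 1.2816)² σ²/δ² = 2 × 10.51 × 1.0/0.36 = 58.4, so 59.

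With dropout: 59/0.9 = 65.6, so 66 per arm and 132 in total. This matches. A two-sample t-test with 59 evaluable per arm has 89.8% power. The arithmetic is sound for its inputs.

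**2. Set the inputs against the schedule.**

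| Month | Experimental arm | Control arm | Named as primary time in |
|---|---|---|---|
| 0–4 | corticosteroids + RASBs | RASBs alone | month 4: synopsis, 4.4 |
| 6 | RASBs alone for 2 months | corticosteroids + RASBs (all patients in Section 3 and the synopsis; those meeting the condition in Section 1.2) | 6, 6.4, synopsis sample size |
| 8 | RASBs alone for 4 months | end of scheduled corticosteroid period | synopsis (non-responders), 4.4 |

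The contrast in the planning assumption, RASBs with corticosteroids against RASBs alone, is intact for every patient only up to month 4.

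**3. Show how power depends on the month-6 difference.** The protocol gives no expected difference with control patients on corticosteroids, so this is illustration only. Let c be the share of the 0.6 g gap that the control arm has closed by month 6. Then δ = 0.6(1 − c), and the t-test non-centrality with 59 per arm is δ√(59/2) = 5.43δ.

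| c (assumed) | δ (g/24 h) | 5.43δ | Power |
|---|---|---|---|
| 0% | 0.60 | 3.26 | about 90% |
| 25% | 0.45 | 2.44 | about 68% |
| 50% | 0.30 | 1.63 | about 37% |
| 75% | 0.15 | 0.81 | about 13% |

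**4. Check whether moving to month 4 preserves the 90%.** The protocol gives no 4-month difference or SD either. If 0.6 g and SD 1.0 hold there, power is 90% with 132 patients. If the 4-month difference were 0.5 g (assumed, SD 1.0), 59 per arm would give about 77%; 90% would need 2 × 10.51/0.25 = 84.1, so 85 evaluable per arm, or 85/0.9 = 94.4, so 95 per arm and 190 in total.

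**The case against.** The best reply comes from the protocol's own hypothesis. Sections 1.1, 3 and 6.1 argue that active lesions become chronic within 3 to 6 months and then respond little to corticosteroids. On that view, corticosteroids started at month 4 would add little by month 6 and the 0.6 g gap could persist. That stands as a possibility, and it is why 0% catch-up belongs in the table. It does not rescue Section 6, which does not invoke the hypothesis: it simply describes the control patients as on RASBs alone.

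A second reply is that Section 2.1 compares strategies, early corticosteroids against RASBs followed by corticosteroids, so corticosteroid use in the control arm is part of the comparator and not contamination. This also stands. A reader might infer that a null result at month 6 would be uninterpretable, or that the effect would change sign. The documents support neither: a null would mean that early start showed no advantage over sequential care at that time. Even so, a strategy comparison would need its own planning figure, and none is given.

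Third, Section 1.2 makes control-arm corticosteroids conditional, so some control patients may still be on RASBs alone at month 6. A reader might infer that the planned contrast does not exist at all; under Section 1.2 it is mixed, not absent.

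Finally, as extracted, Figure 2A seems to mark the primary endpoint from month 6 onward. The table may have been damaged in extraction, so it is given no weight either way.

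**Conclusion.** The point holds. The ACiGaN primary time point is contradictory within the protocol, and the powered and analysed time does not match the comparator assumed for it. It should be resolved before the primary analysis is fixed.

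The size of the power loss cannot be derived from the document. The stated 90% is unsupported at month 6; it would go too far to call it false, because the month-6 difference is unknown. The range from about 90% down to 13% rests on assumed catch-up of 0% to 75%, SD 1.0 and 59 evaluable patients per arm. Equally, 90% at month 4 is conditional on inputs that the protocol does not yet give for that time.

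**What to change.** - **One primary time point.** Name a single ACiGaN primary time and use it in the synopsis and Sections 4.4, 6, 6.4 and 6.5. Month 4 is the time that matches the RASBs-alone assumption; it is already a scheduled visit and a listed endpoint time. Delete the 6-month definition.
- **Month 8.** Keep it as a named secondary comparison of early against delayed corticosteroids, and resolve the synopsis wording that confines it to non-responders.
- **Power.** Restate the expected change in each arm, the SD and their source for the chosen time. Say that 132 patients give 90% power only if 0.6 g and SD 1.0 are justified there; otherwise restate the power (about 77% at 0.5 g) or the sample size.
- **Interim.** In Section 7.3, tie the ACiGaN interim to the same time point and state it separately from CHRONiGaN, whose primary time in Section 4.4 is 10 months.
- **Schedule wording.** Reconcile the conditional control-arm corticosteroids in Section 1.2 with the unconditional sequence in Section 3 and the synopsis. Which of them is right is for the sponsor to settle.

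The cost is a protocol amendment and a newly sourced planning assumption. No visit needs to be added for month 4. Whether more patients are needed depends on what the 4-month evidence supports.

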6.1 Recruitment

Rationale: In some RCTs (22,23) IgAN patients received three - six months of RASBs treatment before their enrollment for corticosteroid therapy. In our opinion this approach is not correct because the active renal lesions evolve in the chronic stage and are no-responsive to corticosteroid therapy. Therefore, the aim of our RCT is early treatment of the active renal lesions because they are responsible for altered GFR and proteinuria.

Recruitment: IgAN patients will be enrolled within 2-4 weeks from the kidney biopsy in renal centers. The kidney biopsy will be scored according to the Oxford classification (6-8) because it is a simple method for predicting renal outcomes and for scoring active and chronic renal lesions (46). Therefore, the kidney biopsy will be the principal key-note, not only for diagnosis but also for personalized therapy, because active renal lesions (E1,C1) will be treated with immediate corticosteroid therapy before lesions become chronic.

The kidney biopsy will be analyzed using digital histopathologic analysis coupled with machine-learning tools. At least eight glomeruli will be available for a correct diagnosis. Immunofluorescence technique will be used to determine the relevance of mesangial IgA deposits in the glomeruli. Renal tissue sections will be stained with hematoxylin and eosin, periodic acid-Schiff and methenamine silver. The last edition of the Oxford classification (MESTC) (8) will be used for the scoring of the renal lesions. Active renal lesions are endocapillary (E) and extracapillary (C) proliferative lesions while T lesions (T1,2) are expression of chronic renal lesions and severe outcome (46-49). Other histological lesions will be evaluated as fibrinoid necrosis, global glomerulosclerosis and arteriolosclerosis.

Three independent renal pathologists, blinded to the study results, will score the lesions in the kidney biopsy using the Aperio System. The histology report will be necessary for the enrollment of patients. No larger RCT has confirmed that the disease improves when clinical decisions are made in a short time in the presence of the MESTC score.

-Serum creatinine. Creatinine will be measured using enzymatic methods calibrated to the National Institute of Standards and Technology Liquid Chromatography Isotope Dilution Mass spectrometry method. Estimated (e) GFR creatinine will be estimated by the CKD-EPI formula (50). Moreover, we will calculate the slope of acute, chronic and total eGFR (51). Patients, categorized in CKD stage 1 to 3, will be included in the clinical study.

-Proteinuria. Patients will collect 24 hour urine for proteinuria and creatininuria. Values of >0.5 g/day will be considered abnormal. We will measure the time-average proteinuria (TA-P) (52) and the slope of proteinuria (53).

Serum creatinine, proteinuria, age and hypertension have a lower weight when histological lesions are not considered. This finding highlights the importance of the kidney biopsy, not only for diagnosis but for personalized treatment.

-Blood hypertension is defined when values are > 130/80 mmHg or in subjects treated with anti-hypertensive drugs. Treatment will also be conducted in hypertensive patients with blood pressure >130/80 and daily proteinuria more than 0.5 g. Sodium restriction is necessary.

